NCM4HIV capitalizes on the "come as you are" approach endorsed in the Clinical Guidelines⁷⁹ put forth by the National Healthcare for the Homeless Council (NHCHC) and aligns with NIH HIV/AIDS High Priority Research Area for reducing HIV through behavioral prevention and access to services in high HIV prevalence and substance-using populations. Additionally, NCM facilitates coordination with YEH service providers to meet mental health, substance use, and housing service needs and connects youth to the healthcare services at the Health Care for the Homeless Program (HCHP), such as HIV and STI testing and treatment. If efficacious, we will

partner with the NHCHC to disseminate the program across its approximately 300 programs and 3,300 clinics that provide care for people experiencing homelessness (see Letters of Support [LOS]).

Objectives

Aim 1: Determine whether the enhanced NCM intervention increases uptake of HIV prevention strategies (PrEP and nPEP uptake, HIV testing, STI screening and treatment, and condom use) when compared with wait list control youth (N=450; aged 16-25 years) at baseline, immediate post, and 3, 6, and 9 months

H1: Youth receiving NCM will have greater improvements in these outcomes over 9 months than control youth

Aim 2: Determine whether NCM4HIV improves mental health, substance use, and housing status when compared with wait list control youth at baseline, immediate post, and 3, 6, and 9 months

H2: Youth receiving NCM will have greater improvements in these outcomes over 9 months than control youth

[figure not shown]
Exploratory Aim: Determine if health seeking, coping, HIV risk perception, PrEP/nPEP barriers/facilitators, and condom self-efficacy mediate intervention effects on PrEP/nPEP uptake, HIV/STI testing, and condom use

Study Design

Figure 2. Study Design

| | Baseline | Intervention | 3 Mon. | 6 Mon. | 9 Mon. | Intervention |
|-------------------|----------------|------------------|----------------|----------------|----------------|--------------|
| Treatment arm | O ₁ | X O ₂ | O ₃ | O ₄ | O ₅ | |
| Wait list control | O ₁ | O ₂ | O ₃ | O ₄ | O ₅ | X |

Figure 3. Study Design

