| HIV/STI Test Uptake | Rapid HIV test; Gonorrhea, Chlamydia, Syphilis test | NA |
| Aim 2 Outcomes | | |
| Mental Health | Brief Symptom Index-18 ^{2,3} | 0.80 |
| Housing Status | In a shelter, apt/house, with someone, outside, in a car...? | NA |
| Substance Use | TCU Drug Screen II ^{4,5} | 0.89 |

| Exploratory Outcomes (possible mediators based on CHSCF; see Figure 1) | | |
|--|---|------|
| Healthcare Engagement | Healthcare clinic visit adherence ⁶ | NA |
| Condom Use Self-Efficacy | Condom Use Self-Efficacy Scale ⁷ | 0.91 |
| HIV Risk Perception | Perceived Risk of HIV scale ⁸ | 0.88 |
| PrEP Facilitators & Barriers | Facilitators and Barriers to PrEP Use ⁹ | NA |
| Health Seeking | General Help Seeking Questionnaire ¹⁰ | 0.83 |
| Coping | Coping Inventory for Stressful Situations-Adolescent ^{11,12} | 0.92 |

For Aim 1, we anticipate having 87% power (95% CI: 84.8, 89.0) to detect the intervention effect on the reduction of condomless sex. Alpha was set at .05 and the power calculation was conducted using the SIMR package¹⁵ by 1000 Monte Carlo simulations with a generalized linear mixed model design that included a random intercept per participant. Data for the simulation were generated with compound symmetric covariance structure in the SIMSTUDY package by assuming that 79% of participants are sexually active and the probability of condomless sex will reduce modestly from 0.7 to 0.4 in the intervention group. The probability was conservatively assumed to decrease to 0.55 in the control group due to the potential for a placebo and/or contamination effect. The effect sizes and powers for HIV testing and STI screening and treatment outcomes are anticipated to be of similar magnitude to the condomless sex outcome. For the PrEP uptake outcome, it was assumed that rates would change from 2% to 4% in the control group and to 24% in the intervention group, for which the simulation resulted in 99% power (95% CI: 94.6, 99.9). Power analysis for the continuous instrument scores of Aim 2 indicates that a sample size of n = 315 will provide 80% power for the interaction of time and arm in a repeated measures model when the effect size is f= .11, a small effect size. This calculation assumes a correlation between repeated measures of r = .50.

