Analysis Plan by Study Aim. Descriptive statistics will be calculated by study arm for baseline demographic characteristics, including age, gender identity, race/ethnicity, sexual orientation, educational level, and employment. However, random allocation of the participants to the intervention and control study arms will make it unlikely that there will be significant differences between the groups for baseline variables that could confound the results. Descriptive statistics will be calculated for all measures at each time point. We expect missing data to be minimal. Obvious errors will be corrected; those that cannot, will be set to missing. Missing data on the instruments will be replaced using single imputation with case mean substitution (i.e., replacing a participant's missing items with that participant's mean item score).¹⁶ Reliability estimates of the study instruments will be computed with Cronbach's alpha ($\geq .70$ will be considered acceptable for internal consistency).¹⁷ Analysis for this study will be based on the intent-to-treat principle.¹⁸ **Aim 1:** Generalized estimating equation (GEE) analysis will be used to compare the groups' changes over time in the dichotomous outcomes - PrEP uptake, nPEP uptake, condom use, and HIV/STI testing – assessed immediately post intervention and at 3-, 6-, and 9-months. The effects to be tested in the model will include time, study arm, and the interaction of time and study arm. **Aim 2:** GEE with normal distribution and identity link will be used to compare the intervention arm to the control arm over time with respect to mental health symptoms measured with the Brief Symptom Index, substance use, and number of homeless days in the past month. In case distributional assumptions are not met, Poisson link may be used for the number of homeless days and substance use days. The effects to be tested will include time, study arm, and the interaction of time and study arm. Time will be treated as a continuous variable unless nonlinearities are present, in which case it will be treated as a categorical variable. Hypothesis 1: Intervention youth will have increased PrEP/nPEP uptake and adherence, condom use, STI/HIV testing and treatment compared to wait list control youth. Hypothesis 2: YEH Intervention youth will have decreased mental health symptoms and substance use and report fewer nights on the street compared to waitlist control youth. **Exploratory Aim:** To explore for mediation of the variables in the Comprehensive Health Seeking and Coping Framework,

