
instrument scores for the secondary outcomes including health seeking, coping, HIV/PrEP knowledge, and condom self-efficacy (see Table 2) will be examined as potential mediators in the path between the intervention and the outcome. Each of these indirect paths will be tested separately in multilevel (2-1-1) mediation models¹⁹ calculated in Mplus software.²⁰ The within-subject level in the mediating variable and the outcome (condomless sex) will be collapsed by taking the mean difference centered on each subject's baseline measurement. After collapsing the finest level, the intervention may be considered as a level 2 variable (i.e. between study arms) and the mediators and outcomes will be level 1 variables (subject-level).

Sex as a variable. In each of the analyses for Aims 1, 2, and the exploratory aim, we will assess for differences by sex (operationalized as gender identity, not biological sex). If the power is not adequate to assess for sex differences, we will control for sex differences in the analyses.

Equations for the models.

GEE models for aims 1 and 2 may be expressed as:

$$g(\mu_{ij}) = X_{ij}^k \beta^k,$$

where μ_{ij} is the mean response for subject i at time j , and g is a link function that is selected to be appropriate for the type of response variable (normal, binary, or Poisson). The predictors are denoted by X_{ij}^k , where the index k is used to distinguish between each predictor. The predictors include the study arm (control/treatment), the time, and the interaction of time and study arm. Covariates, such as sex, may be included if the randomization has not resulted in uniform distributions in each study arm. Solution of the GEE estimating equation will result in estimated values of the coefficients β^k .

Ethics

Adequacy of Protection Against Risks.

General Recruitment and Informed Consent.

Participant recruitment will begin after obtaining UTHealth IRB approval.

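### Aim 1 names no deciding test or visit set, and if the linear time-by-arm term decides, the stated 87% and 99% powers are not supported at within-person correlations up to about 0.5

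*Combined protocol and SAP*

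**What the plan says.** Under Analysis Plan by Study Aim, Aim 1 uses GEE to compare the arms' "changes over time in the dichotomous outcomes", "assessed immediately post intervention and at 3-, 6-, and 9-months". It continues: "The effects to be tested in the model will include time, study arm, and the interaction of time and study arm". Equations for the models repeats the list: "The predictors include the study arm (control/treatment), the time, and the interaction of time and study arm". Neither place names a deciding term.

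The visit set differs between sections. Aim 1 in the Objectives makes the comparison "at baseline, immediate post, and 3, 6, and 9 months", and Figure 2 shows five assessments including baseline.

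The hypotheses point in different directions. H1 in the Objectives reads "Youth receiving NCM will have greater improvements in these outcomes over 9 months than control youth", which suggests a difference in change. Hypothesis 1 in the Statistics section reads "Intervention youth will have increased PrEP/nPEP uptake and adherence, condom use, STI/HIV testing and treatment compared to wait list control youth", which suggests a difference between arms.

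Under Sample Size and Power Calculations, "we anticipate having 87% power (95% CI: 84.8, 89.0) to detect the intervention effect on the reduction of condomless sex"; 99% is given for PrEP uptake. A random-intercept mixed model and a compound symmetric structure are mentioned, but no tested term, correlation value or time course. For Aim 2 the same section does name the time-by-arm interaction and a correlation of .50. The rule that time is continuous unless nonlinear sits in the Aim 2 text.

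**The concern.** Three effects, two possible visit sets and two possible forms of time give several Aim 1 tests of very different power, and nothing in the plan settles which one counts before the data are seen. The wording on change over time leads an analyst towards the interaction. For an effect that appears early and is then held, that test uses the data poorly: the arms separate once and stay apart, so little or no slope difference remains to detect. A real effect of the planned size could then be declared absent, or the deciding term could be picked after the results are known.

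**Working it through.** **Inputs from the plan.** Randomised 450; 450 × 0.70 = 315 (210/105). Condomless sex: 315 × 0.79 = 249 (166/83), rates 0.70 to 0.40 against 0.70 to 0.55. PrEP uptake: 2% to 24% against 2% to 4%. Alpha .05.

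**Assumed.** Two-sided test; equally spaced visits; effect timing; Aim 1 correlation. The only correlation in the documents is .50, for Aim 2.

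**1. The plan's own figures.** They cannot be reproduced exactly without the missing inputs, but an arm comparison can match them. For 0.55 against 0.40 at one visit, the variance of the difference is 0.2475/83 + 0.24/166 = 0.004428. Averaged over four visits with exchangeable correlation r, it is multiplied by (1 + 3r)/4. Power is Φ(0.15/SE − 1.96):
- r = 0.20: SE 0.0421, power 94.6%
- r = 0.36: SE 0.0480, power 87.8%
- r = 0.50: SE 0.0526, power 81.4%

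So 87% fits an averaged arm contrast at r of about 0.36 if the effect is complete at the first post visit. A final-visit comparison gives 61% (N = 249), 71% (N = 315) or 86% (N = 450). For PrEP uptake at N = 315 it gives 99.9%.

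**2. Interaction on the four post visits only, effect held.** The log-odds gap is ln(0.55/0.45) − ln(0.40/0.60) = 0.606 at every visit. Its slope is zero, so the test rejects at about alpha.

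**3. Linear interaction with baseline, by hand on the rate scale.** With visits 0 to 4, Σ(t − 2)² = 10 and the variance of the slope difference is 0.004428(1 − r)/10.
- Effect complete at immediate post: slope 0.15 × (−1 + 0 + 1 + 2)/10 = 0.030. For r = 0.2, 0.5, 0.7, z = 1.59, 2.02, 2.60 and power is 36%, 52%, 74%.
- Straight-line effect: slope 0.15/4 = 0.0375. Power is 51%, 71%, 90%; the large-sample logit GEE gives 48%, 67%, 87%.

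**4. Simulation.** Exchangeable logit GEE with robust SE; compound-symmetric latent normal cut to binary (my assumption; the plan states only the covariance structure); latent correlation 0.3–0.7, observed about 0.2–0.5 for condomless sex; 2000 runs per scenario. Ranges cover 9-month completers and available-case data. Power, %:

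| | Full at immediate post, held | Half, then full from 3 months | Straight line on logit | Late (0, 1/3, 2/3, full) |
|---|---|---|---|---|
| Condomless sex, linear interaction with baseline | 36–61 | 50–73 | 46–69 | 54–71 |
| Condomless sex, post-only interaction | 4–6 | 14–22 | 27–44 | 45–61 |
| Condomless sex, post-visit arm contrast, baseline-adjusted | 93–99 | 87–92 | 63–68 | 46–51 |
| PrEP, linear interaction with baseline | 23–35 | 36–51 | 69–82 | 69–80 |
| PrEP, post-only interaction | 5–7 | 9–12 | 50–62 | 46–61 |
| PrEP, post-visit arm contrast, no covariate | 99–100 | 99–100 | 99–100 | 99–100 |

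A separate simulation of completers gave 32–68% and 20–75% for the linear interaction, hence the overall 32–73% and 20–82%. There the contrast gave 97–100% for PrEP uptake. The plan's random-intercept logistic model in place of GEE gave 31–67% for condomless sex.

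**5. Where the shortfall shrinks.**
- By large-sample approximation, condomless sex reaches 87% for a gradual effect at r of about 0.70 (N = 249) or 0.62 (N = 315, ignoring the 79% factor), and at about 0.45 for N = 315 with abrupt onset at 6 months. Simulations at observed r of about 0.6 gave only 59–70% at N = 249.
- Abrupt onset at 6 months with r = 0.5 gave 81–82% for condomless sex (249 completers or available-case) and 83–91% for PrEP uptake: above the four-course ranges, still below 87% and 99%.
- Categorical time for PrEP uptake with an immediate step gave about 48–64% (N = 315). This depends on how empty cells are handled: the chance of no baseline PrEP user among 105 controls is 0.98^105 = 12%.

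**The case against.** The stated powers may be correct. The plan never says they belong to the interaction, and step 1 shows that an arm contrast can produce them. This stands: a reader might infer that 87% and 99% are miscalculated, and the documents do not support that.

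The shortfall is conditional. The Aim 1 correlation, time course and analysed N are unstated, and a high enough correlation lets the condomless-sex interaction approach or reach 87%. This also stands, and it is why the claim is limited to r up to about 0.5.

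The lowest PrEP figures come from a linear-time test of a step effect. If the plan's nonlinearity rule extends to Aim 1, categorical time would replace it. Fair; power still falls well short of 99%.

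The near-alpha result requires leaving baseline out, which the Objectives and Figure 2 argue against. True, but the Aim 1 analysis text lists only post-intervention visits, so that reading has to be closed off.

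One might also infer that HIV testing uptake starts near 100% and can only fall. HIV/STI Test Specimens does place an HIV screen within eligibility screening, but it also says testing is offered at baseline, and the stepwise and telephone screening descriptions list no HIV test. Only a conditional statement holds: if the eligibility or baseline test counts as uptake, change from baseline is uninformative.

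Finally, naming the interaction in advance would also remove the ambiguity. It would, but the power would then have to be restated for it.

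**Conclusion.** The gap is real and should be fixed: Aim 1 has no deciding term and no consistent visit set, and its power statement cannot be tied to a test. If the linear interaction with baseline decides, power is about 32–73% for condomless sex and 20–82% for PrEP uptake. This rests on the four assumed time courses, observed correlation up to about 0.5, and 249 (condomless sex) or 315 (PrEP) completers or the matching available-case data.

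A reader might infer that an arm contrast wins unless the effect starts late. That is too strong for condomless sex. The contrast is clearly better when most of the effect is present by immediate post or 3 months. For a gradual effect (58–68%) it is ahead at low correlation and about ties at higher correlation. For late onset it is equal or worse (46–53% against 52–71%). For PrEP uptake it was better in all four courses. The one exception found was abrupt onset at 6 months with r = 0.5, where it gave 79–81% against 83–91%. nPEP and STI testing were not simulated.

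**What to change.** 1. In the Aim 1 analysis text, name as the deciding test the 1-df arm effect averaged over the four post-intervention visits, with visit categorical. State that the continuous-unless-nonlinear rule does not govern this test.
2. Adjust condom use for its baseline value, with a missing-baseline category so that participants without one are kept. Use no baseline covariate for PrEP or nPEP uptake. Fix the rule for HIV and STI testing in advance, including whether eligibility or baseline tests count as uptake.
3. Report arm by visit as secondary.
4. Reword H1 in the Objectives and Hypothesis 1 in the Statistics section to match this contrast.
5. Restate Aim 1 power with its tested term, N, correlation and time course. If the team expects a late onset for condomless sex, it should name the interaction in advance instead and re-run power for it.

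The cost is SAP wording and a repeat of the power simulation; no new visits or data are needed. Two downsides should be accepted openly: restated condomless-sex power may be below 87%, and the simulated type I error of the PrEP contrast was slightly high at 5.7–5.8% (5.0–5.5% for condomless sex).

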The YWG (n=10) will be currently or formerly YEH aged 16-25 years who will meet monthly in YR-1 then, if needed, to achieve the study aims and will be compensated at \$25 per working session. Lunch will be provided during the sessions. YWG members will assist in the development of study procedures, survey items, and recruitment materials to provide the experiential context of HIV risk. The RC and PI will co-chair YWG sessions and they will last 1-2 hours.

Intervention Description

Table 1. Differentiation between Usual Care and the NCM4HIV Intervention

| Current Usual Care Services Available | Expanded NCM4HIV Components |
|---|---|
| Housing, food, and clothing needs, health assessment, basic healthcare, limited anticipatory guidance, mental health counseling, substance use treatment referrals, PrEP/nPEP referrals | Personalized HIV prevention education, behavior goal-setting, behavioral self-monitoring, PrEP eligibility screening, PrEP/nPEP services (labs, medication), healthcare planning/coordination, MI counseling approach, assisting with cognitive appraisals (clarifying misconceptions), promoting health seeking and coping behaviors that incorporate the situational, personal, social, and resource needs affecting health |

An individual intervention design was chosen due to the heterogeneity of YEH and their risk behaviors and the challenges associated with group session designs including low attendance.¹⁰⁴

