
Table 2. Team Developed Enhanced NCM HIV Prevention Intervention Session Description

| # | Session Title | CHSCF Construct | Motivational Interviewing Discussion Topics | Session Goals |
|----|----------------|-----------------|---|--------------------|
| 1. | Introduction & | Situational, | Review HIV risk behaviors & prevention | Establish rapport; |

| | | | | |
|----|--|--|---|--|
| | Needs Assessment | personal, social factors, & resources | strategies (condoms, HIV/STI testing, treatment, PrEP, nPEP) knowledge, attitudes, beliefs, self-efficacy | assess HIV risk, PrEP eligibility |
| 2. | HIV Prevention Strategies & Goal Setting | Nursing goals | Review personal HIV risk; use MI to discuss strategies to increase the safety of sexual activity, evoke change talk | Select HIV prevention behavioral goals and action plan |
| 3. | Behavioral Feedback & Goal Alignment | Health seeking & coping behaviors | Identify gaps between goals & behaviors (e.g., self-management, coping, health care engagement), evoke change talk | Revise/reinforce plan to meet/maintain HIV prevention goals |
| 4. | Addressing Facilitators & Barriers | Perceived behavior compliance & coping effectiveness | Review goals and action plan; use MI to discuss personal HIV prevention behavioral change facilitators & barriers, evoke change talk | Revise/reinforce HIV prevention goals and action plan to increase facilitators |
| 5. | Establishing a Medical Home | Immediate health outcomes | Review goals and action plan; discuss local clinic preferences and schedule well-check as indicated, evoke change talk and behavioral maintenance | Revise/reinforce HIV prevention goals, action plan, follow-up care plan |
| 6. | Moving Toward Health & Wellbeing | Long-term health outcomes | Review goals and action plan; identify additional health, housing, work, and education needs/goals, evoke change talk and behavioral maintenance | Reinforce HIV prevention behavioral goals and action plan |

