One focus of the investigator meetings will be to continuously monitor and develop strategies to prevent adverse reactions, monitor the research staff, and protect data integrity. Accrual data will be reviewed by the team and the UTHealth IRB. The study team will make amendments to the protocol should accrual fall below 15% of the target, or should drop-outs exceed projections by 15%. This will include the addition of recruitment sites.

Statistics

Randomization. Participants will be randomly assigned to the intervention or wait list control arm using a computer-generated blocked 2:1 allocation; 300 participants will be in the intervention arm and 150 will be in the wait list control arm (see Figure 3). Participants will be told which group they are in after completing the baseline survey and will receive a study-issued phone with programmed YEH resources unless they prefer to use their own phone. In this case, the behavioral feedback app will be loaded onto their personal phone for those in the intervention arm, and these youth will be provided with a list of YEH services.

Study Design.

| | Baseline | Intervention | 3 Mon. | 6 Mon. | 9 Mon. | Intervention |
|-------------------|----------------|------------------|----------------|----------------|----------------|--------------|
| Treatment arm | O ₁ | X O ₂ | O ₃ | O ₄ | O ₅ | |
| Wait list control | O ₁ | O ₂ | O ₃ | O ₄ | O ₅ | X |

Sample Size and Power Calculations. The primary endpoint is the efficacy of NCM to increase PrEP and nPEP uptake, HIV testing, STI screening, and condom use. Conservatively assuming an attrition rate of 30% at 9 months, the final sample size will be 315, with the 2:1 randomization allocation providing for 210 participants in the intervention arm and 105 in the control arm. We estimate a retention rate of 70% based on study resources, community partnerships and support, the use of study-issued phones, the use of increasing follow-up incentives. This retention rate is substantially lower than the rate reported for other longitudinal YEH studies that have retained 88-89% ^{13,14} of youth to be very conservative in our retention estimation.

Table1. Outcome Measures by Study Aim

| Construct | Scale/Measure | Alpha |
|-----------------------|---|-------|
| Aim 1 Outcomes | | |
| PrEP/nPEP Uptake | PrEP uptake; nPEP uptake (NCM report, chart review) | NA |
| Condom Use | Youth Risk Behavior Survey; ¹ (condom use at last sex) | NA |

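### Each candidate mediator is tested only in its own model, so one with no effect of its own can be named a mediator if the arm moves it and it correlates with a true mediator

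*Combined protocol and SAP*

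**What the plan says.** The Objectives set the exploratory question: "Determine if health seeking, coping, HIV risk perception, PrEP/nPEP barriers/facilitators, and condom self-efficacy mediate intervention effects" on PrEP/nPEP uptake, HIV/STI testing and condom use.

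The method is under Statistics, Analysis Plan by Study Aim, Exploratory Aim. There, "instrument scores for the secondary outcomes including health seeking, coping, HIV/PrEP knowledge, and condom self-efficacy (see Table 2) will be examined as potential mediators", and "Each of these indirect paths will be tested separately in multilevel (2-1-1) mediation models". The repeated measures of the mediator and of condomless sex "will be collapsed by taking the mean difference centered on each subject's baseline measurement", which leaves one change score per participant.

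The intervention is meant to act on several candidates at once. Table 1 of the Intervention Description lists among its components "promoting health seeking and coping behaviors that incorporate the situational, personal, social, and resource needs affecting health", and Table 2 gives "Health seeking & coping behaviors" as a single construct for session 3.

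The documents describe no model with several mediators and no adjustment of one mediator for another. They assume no correlation between mediators, and they set no rule for reading a positive single-mediator result.

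**The concern.** Randomisation protects the path from arm to mediator. It does not protect the path from mediator to outcome. In a one-mediator model that second path is only the arm-adjusted association of the candidate with condomless sex. If the candidate has no effect but its change correlates r with that of a true mediator, the association is about r times the true slope, not zero.

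The null of each test is composite: the arm does not move the candidate, or the candidate is unrelated to the outcome within arm. A bystander escapes both halves when the arm moves it and it travels with a true mediator. Shared sessions make the first condition plausible for several candidates.

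What is at stake is which mechanism the exploratory aim names. Indirect effects from separate models also overlap, so they can be neither summed nor ranked.

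**Working it through.** The plan gives no power or error rate for the mediation tests, so there is no figure to reproduce.

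**Inputs from the documents** (Sample Size and Power Calculations)
- "Conservatively assuming an attrition rate of 30% at 9 months, the final sample size will be 315", split 210 and 105. Check: 450 × 0.70 = 315; 315 × 2/3 = 210.
- Alpha 0.05, stated for Aim 1 only ("Alpha was set at .05 and the power calculation was conducted using the SIMR package"). Two-sided 0.05 is assumed for mediation.

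**Assumptions not in the documents**
- The arm shifts both the true mediator M1 and the bystander M2 by a = 0.3 or 0.5 SD.
- M1 has a standardised effect b of 0.2 to 0.4 on the outcome; M2 has none.
- The within-arm correlation r of their changes is 0 to 0.5.
- Mediation is declared when both paths are significant (joint-significance test).

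**Path from arm to M2.** SE = √(1/210 + 1/105) = 0.1195. For a = 0.3, z = 2.51 and power is 0.709. For a = 0.5, z = 4.18 and power is 0.987.

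**Path from M2 to outcome, separate model.** Slope = r·b and SE = √[(1 − (r·b)²)/312]. The chance of significance is Φ(z − 1.96) + Φ(−z − 1.96). Multiplying the two chances gives the false declaration rate:

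| r | a | b | r·b | z | P(path 2) | Declared |
|---|---|---|---|---|---|---|
| 0.2 | 0.3 | 0.2 | 0.04 | 0.71 | 0.109 | 8% |
| 0.2 | 0.5 | 0.4 | 0.08 | 1.42 | 0.294 | 29% |
| 0.3 | 0.3 | 0.2 | 0.06 | 1.06 | 0.186 | 13% |
| 0.3 | 0.5 | 0.4 | 0.12 | 2.14 | 0.569 | 56% |
| 0.5 | 0.3 | 0.2 | 0.10 | 1.78 | 0.427 | 30% |
| 0.5 | 0.5 | 0.3 | 0.15 | 2.68 | 0.764 | 75% |
| 0.5 | 0.5 | 0.4 | 0.20 | 3.61 | 0.950 | 94% |

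Simulation of the same design (2,000 runs per setting) gives 10-31%, 14-55% and 30-94% for the three correlations, within about 2 points of the formula. The Sobel test gives lower rates, 3-87% over the same grid.

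**Joint model.** The slope of M2 given M1 is zero, so the rate is 0.05 × 0.709 = 3.5% or 0.05 × 0.987 = 4.9%. Simulation gives 3-6%.

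**Boundary checks.** At r = 0 the separate model gives the same 3.5-4.9% (simulation: about 6% or less). If the arm does not move M2, the rate is at most 0.05 × 1 = 5%; for b = 0.3 and r = 0.5 it is 0.05 × 0.764 = 3.8%.

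**Check on the plan's own outcome.** A second simulation used the sexually active share (0.79 × 315 ≈ 249, split 166 and 83), condomless sex falling from 0.70 to 0.40 against 0.55, and the mean of four follow-ups minus baseline. It assumed that the true mediator is shifted 0.5 SD and carries half or all of the 15-point effect, with a latent intraclass correlation of 0.4. A bystander shifted 0.5 SD was declared in 30-64% of trials at r = 0.3 and 65-95% at r = 0.5 (joint significance). One shifted 0.3 SD was declared in 20-41% and 42-61%. Joint models gave about 3-6%.

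**Power cost for the true mediator.** At b = 0.2 and r = 0.5, z falls from 0.2/√(0.96/312) = 3.61 to 0.2/√[0.96/(311 × 0.75)] = 3.12. The chance falls from 0.950 to 0.877. With a = 0.5 the loss is (0.950 − 0.877) × 0.987 ≈ 7 points. Simulated losses were 0-8 points for r up to 0.5.

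**The case against.** The strongest objection is that correlated candidates may form a causal chain. Table 2 lines the sessions up with the framework's constructs in sequence. Suppose the arm moves M2, M2 moves M1 with standardised slope d, and M1 moves the outcome. Then M2 really does carry the effect. Its slope in the separate model is d·b, so the table applies with d in place of r. At b = 0.3 the separate model finds M2 in about 25% of trials (a = 0.3, d = 0.3) to 75% (a = 0.5, d = 0.5), while the joint model credits it in only about 4-5%. The data cannot tell a bystander from an upstream mediator. This stands, and it rules out replacing the separate models.

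A reader might infer three stronger things that the documents do not support:
- **That each test's null is simply no association within arm.** It is composite, and a candidate that the arm leaves alone is protected.
- **That most candidates will test positive.** Shared sessions show that the arm may shift several constructs. They say nothing about within-arm correlation, which drives the error and is given nowhere.
- **That the plan promises to isolate the active ingredient.** It calls the aim exploratory and the variables potential mediators. It ties no decision to these tests and does not say that the indirect effects will be added or ranked.

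The exploratory label limits the consequence. It does not supply the missing adjustment or a rule for reading the results.

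**Conclusion.** The point holds in a conditional form and is minor. Tested only separately, a candidate with no effect of its own is over-declared if the arm moves it and its change correlates within arm with that of a true mediator. Under the stated assumptions the excess is modest to moderate at r = 0.2 to 0.3 and large at r = 0.5, and it vanishes at r = 0. Which case applies cannot be known from the documents. The range also depends on the size of the arm's shift, the strength of the true mediator and the test used.

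Only the exploratory aim is affected. A joint model adjusts for the other measured candidates; it does not remove unmeasured mediator-outcome confounding.

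**What to change.** Keep the separate 2-1-1 models and add to the Exploratory Aim paragraph:

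> All listed mediators will also be entered together in one parallel multiple-mediator model per outcome, reporting the total indirect effect and each specific indirect effect with bootstrap intervals. A mediator significant only in its separate model will be reported as a correlate or possible upstream mediator, not singled out as carrying the effect. Separate indirect effects will not be added or ranked.

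The joint model needs one fixed list. At present the Objectives name five candidates, the outcome table six, and the analysis paragraph four by way of example.

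The cost is some SAP wording and one further Mplus model per outcome, on data already planned. Specific effects get somewhat wider intervals: the true mediator loses 0-8 points of power for r up to 0.5. At r = 0.7, in the four-candidate simulation with half the effect mediated (249 participants), power fell from about 96% to 84-86%. An upstream mediator in a chain appears in its separate model and in the total effect but not in its specific effect, which is why the separate models should stay.
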